4 Vermont conducted a pilot clinical trial that examined the feasibility, efficacy, and cost-
5 effectiveness of a smartphone-based financial incentives intervention whereby smoking
6 monitoring and delivery of incentives were completed remotely using a mobile app (DynamiCare
7 Rewards, designed by DynamiCare Health, Inc.). For this pilot trial, pregnant women were
8 recruited via obstetrical clinics and WIC offices in Vermont, as well as Facebook ads deployed
9 nationally. Eligible participants who completed the informed consent process were assigned to
10 one of two conditions: an incentives condition wherein women receive financial incentives
11 contingent on the remote submission of breath and saliva specimens indicating abstinence from
12 recent smoking (described below), or a best practices control condition in which women receive
13 usual care for smoking cessation that is provided at their obstetrical clinics, as well as three brief
14 educational sessions and referral to their state quit line by our research staff. Data from the this
15 trial were promising, with participants in the Best Practices plus Incentives condition
16 demonstrating over three-fold higher quit rates at late pregnancy (~37%) versus Best Practices
17 participants (~11%). [name] and [name] are currently conducting a larger-scale version of
18 this clinical trial.

19
20 One group that is not currently being reached by this highly promising intervention approach are
21 Alaska Native women. Thus, the proposed study seeks to examine the preliminary feasibility
22 and efficacy of this remote, smartphone-based incentives intervention among 60 Alaska Native
23 pregnant women who are current cigarette smokers.

24
25 For inclusion in the study, Alaska Native women must meet the following criteria: (a) ≥ 18 years
26 of age, (b) report being smokers at the time they learned of the current pregnancy, (c) report
27 smoking in the 7 days prior to completing their eligibility screening, (d) ≤ 25 weeks pregnant, (e)
28 speak English, (f) own a smartphone (Android or iOS; 81.8% of pregnant women in wave 1
29 [2013-2014] of the Population Assessment of Tobacco and Health [PATH] reported owning a
30 smartphone). Exclusion criteria include: (a) current or prior mental or medical condition that
31 may interfere with study participation (assessed via self-report during eligibility screening), (b)
32 smoke marijuana more than once each week and not willing to quit (marijuana smoking can
33 inflate breath CO), (c) exposed to unavoidable occupational sources of CO (e.g., car mechanic),
34 and (d) self-report currently being maintained on opioid maintenance therapy (e.g., methadone,
35 buprenorphine).

36
37 Participants randomized to the Best Practices plus Incentives condition will select a quit date
38 (either the first or second Monday following their enrollment), and will submit videos of
39 themselves blowing into a breath CO monitor twice daily during week 1. They will receive
40 incentives for every sample where expired breath CO is ≤ 6 ppm. Beginning in week 2 and
41 extending through week 6, participants will submit videos twice per week (Monday/Thursday)
42 for which they will receive incentives for providing videos of themselves completing saliva
43 cotinine tests indicating smoking abstinence. From week 7 until delivery, participants will
44 submit videos once per week and will continue to receive incentives for saliva cotinine tests
45 indicating no smoking. During the postpartum period, women will submit videos twice weekly
46 for the first 4 weeks and once weekly from weeks 5-12. The first negative breath CO or salivary

1 cotinine sample is worth \$6.25 and each consecutive negative sample will increase the value of
2 the incentive by \$1.00 up to a maximum of \$33.25 per sample. Missed samples or samples that
3 indicate smoking will be worth \$0 and will reset the incentive at its starting value (i.e., \$6.25).
4 However two consecutive negative samples following the slip will restore the incentive to its
5 value before the slip. The maximum earnings in this condition is \$1,620, which is the same as
6 our prior studies adjusting for inflation. A proposed incentive schedule is attached.
7

8 Women in both conditions will complete seven formal assessments of their smoking status
9 during their participation (intake, early pregnancy or 1 month after enrollment, late pregnancy or
10 ≥ 28 weeks gestation, and at 4-, 8-, 12-, and 24-weeks postpartum) along with a treatment
11 acceptability questionnaire and semi-structured interview on barriers and facilitators of treatment
12 engagement. Women will receive \$50 for completing each of these (\$350 total).
13

14 As the proposed study is the first examination of smartphone-based financial incentives for
15 reducing smoking during pregnancy among Alaska Native women, it represents an exploratory
16 study, thus power analyses were not conducted to select the sample size. However, a sample of
17 60 Alaska Native women (30 Best Practices plus Incentives, 30 Best Practices) is consistent with
18 prior pilot studies on this treatment conducted at the University of Vermont ([name] et al., 2004;
19 [name] et al., 2020). This sample size will be sufficient to detect significant differences in
20 smoking abstinence at participants' late pregnancy assessment, and results of this pilot study will
21 be used to inform power analysis calculations in larger grant applications.
22

23 Participants will be recruited from online media outlets (i.e., Facebook) targeting Alaska Native
24 pregnant women. Recruitment materials that we propose posting online are attached. We have
25 also attached the battery of questionnaires that we propose administering at formal assessments,
26 the Research Information Sheet that we will read to participants over the phone to obtain verbal
27 consent to participate in the study, as well as the full consent form that we will mail to them after
28 obtaining their verbal consent to participate.
29
30

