31 PURPOSE AND OBJECTIVES

32

33 Purpose

34 Smoking during pregnancy is the leading preventable cause of poor pregnancy outcomes in the
35 U.S. and other developed countries, increasing risk for pregnancy complications, preterm birth,
36 stillbirth, infant death, impaired lung development, childhood illness and
37 developmental/behavioral problems, and lifelong increased risk for cardiovascular disease,
38 obesity, and metabolic syndrome.¹⁻⁸ Prevalence of smoking during pregnancy among national
39 samples of U.S. pregnant women has remained stagnant at approximately 13% over the past
40 decade.⁹⁻¹⁰ Because risk for maternal smoking during pregnancy is disproportionately high
41 among economically disadvantaged women, it contributes substantially to the problem of health
42 disparities.¹¹⁻¹² Importantly, smoking prevalence is particularly high among Alaska Native
43 women (i.e., ~ 36% ([name] et al. 2018) versus ~ 13% among U.S. pregnant women overall
44 ([name] et al., 2017). Alaska Native women also exhibit unique tobacco use characteristics
45 including use of a homemade smokeless tobacco (Iqmik, Hurt et al., 2009), and very few

1 smoking cessation interventions have been implemented specifically among Alaska Native
2 women ([name] et al., 2010; [name] et al., 2018).
3
4 Existing treatments for smoking cessation among pregnant smokers produce very low quit rates
5 (< 15%) with the exception of financial incentives. Meta-analyses indicate that incentive-based
6 treatments produce the largest effect sizes of any psychosocial or pharmacological intervention
7 for promoting smoking cessation during pregnancy.¹³⁻¹⁴ Additionally, two randomized,
8 controlled trials conducted by the University of Vermont (UVM) demonstrated that incentives
9 significantly increase sonographically estimated fetal growth, increasing abdominal
10 circumference (cm/week), femur length (cm/week), and overall estimated fetal weight compared
11 to control groups that received non-contingent incentives.¹⁵ Retrospective analyses of birth
12 outcome data aggregated across three previous trials from UVM also indicated that incentives
13 significantly increased mean birth weight, decreased the percent of low birth weight deliveries (<
14 2500 g), increased the percent of women breastfeeding through 12-weeks postpartum, and
15 decreased depressive symptoms from birth through 12-weeks postpartum among depression-

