46 incentives intervention for promoting smoking cessation among Alaska Native pregnant women.

1 We will accomplish this aim by randomly assigning 60 pregnant women who smoke to receive
2 best practices for promoting smoking abstinence plus incentives contingent on biochemically
3 verified smoking abstinence or best practices alone. Incentives will be in place from the start of
4 study enrollment through three months postpartum. Primary outcomes will be point prevalence
5 smoking abstinence and continuous abstinence during and following pregnancy. We hypothesize
6 that there will be higher abstinence rates and longer durations of abstinence in the best practices
7 plus incentives versus the best practices control condition.

8
9 **Aim 2:** Evaluate acceptability of the treatment, including barriers to and facilitators of treatment
10 engagement. We will accomplish this aim by assessing treatment enrollment and retention and
11 conducting semi-structured interviews with participants upon treatment completion. During
12 these interviews, participants will be queried about their perceived utility of the incentives for
13 promoting health-related behavior change, and other barriers and facilitators of treatment
14 engagement and success (e.g., social support networks).²¹⁻²² Qualitative research methods will
15 be used to discern general themes.

16
17 Overall, this project has the potential to address disparities in access to efficacious, evidence-
18 based smoking cessation treatments among Alaska Native pregnant women. If the present
19 mobile-phone-based incentives intervention is acceptable and efficacious in this population, this
20 study will provide strong preliminary data for a future R01 proposal to facilitate more
21 widespread dissemination of this innovative treatment model among Alaska Native communities.

22
23 **Objectives:**

24
25 The primary objective is to examine the feasibility, efficacy, and cost-effectiveness of a mobile-
26 phone-based incentives intervention for promoting smoking cessation among Alaska Native
27 pregnant women.

28
29 The secondary objective is to evaluate the acceptability of the treatment, including barriers to
30 and facilitators of treatment engagement.

31
32
33 **METHODS AND PROCEDURES**

34
35 **Study Design:**

36 We are proposing a two condition, parallel groups, randomized controlled pilot study of a
37 mobile-phone-based financial incentives intervention targeting Alaska Native pregnant cigarette

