44 represents the first feasibility and proof of concept assessment to our knowledge, power analyses
45 were not conducted to determine the sample size needed to obtain statistically significant effects
46 on the above outcomes. However, once we complete our assessment of the feasibility and

1 efficacy of smartphone-based financial incentives among this subset of Alaska Native women,
2 such analyses will be conducted to determine the sample size needed in future, larger-scale
3 studies targeting this unique subpopulation.

4

5 **Sample Size Justification**

6 A sample size of 60 Alaska Native women was selected based on initial pilot studies of the
7 financial-incentives-based approach to promoting smoking cessation among pregnant women
8 developed at the University of Vermont ([name] et al., 2004), as well as [name] pilot study
9 of 60 women receiving best practices plus smartphone-based financial incentives or best
10 practices alone, which was sufficient to detect treatment differences during pregnancy and
11 postpartum. This sample size will be sufficient to determine whether the intervention is feasible
12 and effective at promoting late-pregnancy smoking abstinence between Alaska Native women
13 enrolled in the best practices plus incentives versus best practices Control conditions. Results of
14 our assessment will be used to inform power analysis calculations for larger-scale, NIH-
15 supported research proposals focused on smoking cessation among Alaska Native pregnant
16 women.

17

18

19 **RISKS/BENEFITS**

20

21 **Risks**

22 Participants may experience some discomfort arising from nicotine withdrawal. Participants will
23 be informed during the informed consent process that they may experience the following
24 symptoms of nicotine withdrawal: craving cigarettes, restlessness, irritability, increased appetite,
25 increased eating, dizziness, difficulty concentrating, and depressed mood. There is a small risk
26 that participants' electronic information could be accessed thereby affecting confidentiality.

27 There is a risk that women may be uncomfortable answering some of the questions on the formal
28 assessment batteries. There is a risk that use of other combustible tobacco products and/or
29 marijuana during study participation may elevate participants' breath CO levels thereby
30 preventing them from earning incentives during week 1 even if they have quit smoking

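### The protocol says 60 women are enough to detect a late-pregnancy difference and to determine effectiveness, without a power analysis; at its own pilot rates, power is about 68%.

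*Combined protocol and SAP*

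**What the plan says.** Two places deal with sample size, and both follow the same pattern.

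The opening summary calls the study exploratory and disclaims a calculation: "study, thus power analyses were not conducted to select the sample size. However, a sample of" 60 (30 per arm) matches earlier pilots. Its next sentence reads "This sample size will be sufficient to detect significant differences in" abstinence at the late-pregnancy assessment.

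Under Statistical Considerations, the last paragraph of Statistical Methods says power analyses "were not conducted to determine the sample size needed to obtain statistically significant effects". The Sample Size Justification, directly below, says the sample is enough to find out whether the intervention is feasible "and effective at promoting late-pregnancy smoking abstinence between Alaska Native women" in the two conditions.

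The basis offered is precedent. One source is an initial in-house pilot published in 2004, whose rates the protocol does not give. The other is a 60-woman smartphone pilot comparing incentives with best "practices alone, which was sufficient to detect treatment differences during pregnancy and" postpartum. The opening summary reports that second pilot as "demonstrating over three-fold higher quit rates at late pregnancy (~37%) versus Best Practices" participants at about 11%.

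The Objectives section states: "The primary objective is to examine the feasibility, efficacy, and cost-effectiveness of a mobile"-phone-based incentives intervention. Statistical Methods tests end-of-pregnancy abstinence with a C-M-H test and sets alpha at 0.05 for all analyses. It does not say whether tests are one- or two-sided, names no strata, and gives no target power.

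**The concern.** To say that a sample suffices to detect a significant difference is to make a statement about power, and the protocol says power was not assessed. One earlier trial of the same size reaching significance does not show that a repeat probably would. A trial with modest power can succeed once, and the effect it then observes may be too large.

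Omitting a power calculation from an exploratory pilot is defensible. The difficulty is that the text then claims what such a calculation would have had to show. Efficacy is part of the primary objective, abstinence is a primary outcome with a directional hypothesis, and it is tested at 0.05, so the exploratory label does not cover the claim.

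What is at stake is how a null result is read. The protocol justifies separate randomisation by the ways this population differs from the parent trial's, so the pilot effect may not carry over. A reader told that 60 women are enough to determine effectiveness could take a non-significant result as showing that the intervention does not work in this group.

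**Working it through.** The plan states no power figure, so there is none to reproduce. The check asks what power the design has at the protocol's own rates.

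**Inputs from the protocol**
- 30 per arm, N = 60 (opening summary).
- Late-pregnancy abstinence about 37% versus about 11% (opening summary, smartphone pilot).
- C-M-H test, alpha 0.05 (Statistical Methods).

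**Assumptions**
- Two-sided test.
- One stratum, since none is named.
- All 30 per arm analysed.

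**Exact power.** With x and y abstinent of n per arm, m = x + y and N = 2n, the single-stratum statistic is

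C-M-H = (N − 1)·[x(n − y) − y(n − x)]² / [n·n·m·(N − m)].

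Power is the sum of Bin(x; n, p1) × Bin(y; n, p2) over all tables with C-M-H > 3.841.

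| Incentives vs control | Per arm | Power | Basis |
|---|---|---|---|
| 37% vs 11% | 30 | 67.6% | protocol's rates |
| 36.5% vs 11.5% | 30 | 63.9% | rounding, unfavourable |
| 37.5% vs 10.5% | 30 | 71.2% | rounding, favourable |
| 37% vs 11% | 28 / 27 | 63.6% / 61.9% | illustrative pregnancy-loss exclusions; no rate given |
| 37% vs 13% / 15% | 30 | 58.7% / 50.0% | Purpose section puts existing treatments below 15% |
| 30% / 25% vs 11% | 30 | 45.0% / 29.0% | illustrative smaller effect |
| 42% vs 11% | 30 | 80.6% | about where 80% is reached (41.5% gives 79.5%) |
| 37% vs 11% | 40 | 80.5% | about where 80% is reached (39 per arm gives 79.3%) |

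**Cross-check, pooled normal approximation**
- Mean rate (0.37 + 0.11)/2 = 0.24.
- Null SE = √(0.24 × 0.76 × 2/30) = 0.110.
- Alternative SE = √(0.37 × 0.63/30 + 0.11 × 0.89/30) = 0.105.
- Power = Φ[(0.26 − 1.96 × 0.110)/0.105] = 66.2% with unrounded SEs.

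This approximation gives 42 per arm for 80% power, against 40 by exact enumeration.

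**Other tests at 37% vs 11%, 30 per arm.** Fisher's exact test gives 56.6%. A one-sided 0.05 C-M-H test, which the plan does not specify, gives 79.6%.

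**What significance requires.** Suppose 3/30 controls are abstinent.
- 9/30 on incentives: 59 × (9 × 27 − 3 × 21)² / (30 × 30 × 12 × 48) = 59 × 180² / 518,400 = 3.69, not significant.
- 10/30: 59 × (10 × 27 − 3 × 20)² / (30 × 30 × 13 × 47) = 59 × 210² / 549,900 = 4.73, significant.

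**Precision.** 1.96 × 0.105 = 0.206, so the 95% confidence interval at the pilot rates is 26 ± 21 percentage points, about +5 to +47.

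**The case against.** The strongest reply is that the protocol is open about what it is. It describes the study as exploratory, its efficacy aim as preliminary and the work as proof of concept. It says twice that no power analysis was done, and says the results will feed later power calculations. It sets no power target, so calling the sample insufficient relies on an outside benchmark. Read loosely, as meaning that a pilot-sized effect could reach significance, the summary's sentence is true: 11/30 versus 3/30 gives a statistic of 5.86, and 68% power makes detection more likely than not. The 2004 pilot's rates are not given, so half of the stated basis cannot be tested. No sentence says a null result would be read as lack of efficacy.

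Several of these points stand as limits. The 80% benchmark is convention. The scenarios with 25% or 30% on incentives, and with 27 or 28 per arm, are illustrative. A 15% control rate is the bound of the protocol's range, not a value inside it. The misreading of a null result is an inference. No stated figure is miscalculated, and the power of the planned repeated-measures GEE analysis was not examined.

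The main point survives. Saying that the sample will be sufficient promises more than that significance is possible, and a one-in-three miss rate at the pilot's own effect does not support it. General caveats do not cancel a specific claim made straight after them.

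**Conclusion.** The concern holds. The protocol claims enough patients to detect a late-pregnancy difference and to determine effectiveness, without the analysis needed to say so. Its own pilot rates give 67.6% power, or 63.9% to 71.2% across rounding. That rests on a two-sided 0.05 test, a single stratum and no exclusions. Excluding women with pregnancy loss, as planned, or a smaller difference between arms would lower it. The claim that the sample can show feasibility is not disputed, and the sample size itself is not at fault.

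**What to change.** In the opening summary, delete the sentence's claim about detecting significant differences and keep the clause saying the results will inform later power calculations. In the Sample Size Justification, keep the claim about feasibility and delete the claim about effectiveness. Then state what the design offers, for example:

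> With 30 women per arm and a two-sided 0.05 C-M-H test, power is about 68% if late-pregnancy abstinence is 37% versus 11%, and reaches 80% only if it is about 42% versus 11%. The difference will be reported with its 95% confidence interval (about ±21 percentage points at the pilot rates), and a non-significant result will not be read as absence of effect.

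The two deletions alone remove the unsupported claims. The added text tells readers what a null result can support, and it commits the plan to a two-sided test, which it currently leaves open. The power figure assumes all 30 per arm are analysed, which the text should say.

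The cost is wording in two places. Sample size, randomisation, endpoints and tests do not change; the only downside is that the stated property of the design becomes less favourable.

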31 PURPOSE AND OBJECTIVES

32

33 Purpose

34 Smoking during pregnancy is the leading preventable cause of poor pregnancy outcomes in the
35 U.S. and other developed countries, increasing risk for pregnancy complications, preterm birth,
36 stillbirth, infant death, impaired lung development, childhood illness and
37 developmental/behavioral problems, and lifelong increased risk for cardiovascular disease,
38 obesity, and metabolic syndrome.¹⁻⁸ Prevalence of smoking during pregnancy among national
39 samples of U.S. pregnant women has remained stagnant at approximately 13% over the past
40 decade.⁹⁻¹⁰ Because risk for maternal smoking during pregnancy is disproportionately high
41 among economically disadvantaged women, it contributes substantially to the problem of health
42 disparities.¹¹⁻¹² Importantly, smoking prevalence is particularly high among Alaska Native
43 women (i.e., ~ 36% ([name] et al. 2018) versus ~ 13% among U.S. pregnant women overall
44 ([name] et al., 2017). Alaska Native women also exhibit unique tobacco use characteristics
45 including use of a homemade smokeless tobacco (Iqmik, Hurt et al., 2009), and very few

1 smoking cessation interventions have been implemented specifically among Alaska Native
2 women ([name] et al., 2010; [name] et al., 2018).
3
4 Existing treatments for smoking cessation among pregnant smokers produce very low quit rates
5 (< 15%) with the exception of financial incentives. Meta-analyses indicate that incentive-based
6 treatments produce the largest effect sizes of any psychosocial or pharmacological intervention
7 for promoting smoking cessation during pregnancy.¹³⁻¹⁴ Additionally, two randomized,
8 controlled trials conducted by the University of Vermont (UVM) demonstrated that incentives
9 significantly increase sonographically estimated fetal growth, increasing abdominal
10 circumference (cm/week), femur length (cm/week), and overall estimated fetal weight compared
11 to control groups that received non-contingent incentives.¹⁵ Retrospective analyses of birth
12 outcome data aggregated across three previous trials from UVM also indicated that incentives
13 significantly increased mean birth weight, decreased the percent of low birth weight deliveries (<
14 2500 g), increased the percent of women breastfeeding through 12-weeks postpartum, and
15 decreased depressive symptoms from birth through 12-weeks postpartum among depression-
16 prone women.¹⁶⁻¹⁸ Although this evidence-based treatment has demonstrable capacity to reduce
17 smoking and improve birth outcomes, the scalability of this approach is constrained by the
18 frequent clinic visits necessary for biochemical verification of smoking status, which limits
19 access to those in the immediate vicinity of clinics that can provide such care. ***Capitalizing on***
20 ***technological advancements may surmount such access barriers, with the potential to extend***
21 ***the reach of financial incentives to disadvantaged pregnant smokers nationwide.***
22
23 The overarching aim of the parent study is to develop an innovative, efficacious, remotely
24 delivered financial incentives intervention to reduce cigarette smoking during pregnancy.
25 Pilot data from a sample of 60 pregnant women recruited nationally (30 Best Practices plus
26 Incentives vs 30 Best Practices) yielded promising results ([name] et al., 2020). In brief, it was
27 feasible to recruit and retain pregnant smokers in this smartphone-based smoking cessation pilot
28 study, and smartphone-based financial incentives produced significantly higher quit rates during
29 pregnancy and postpartum relative to controls. The proposed study seeks to examine the
30 feasibility and efficacy of this treatment strategy among Alaska Native women, who were not
31 included in completed pilot study or in the larger clinical trial led by [name] and [name]
32 that is currently underway.
33
34 To enable flexible use of the intervention in diverse locations, we use a mobile-phone-based
35 platform for delivering the incentives intervention. The platform involves a Smartphone “app”
36 (DynamiCare Rewards) which uses video capture to verify smoking status via a breath carbon
37 monoxide (CO) monitor along with saliva cotinine test kits, and ensures treatment fidelity by
38 providing automated, immediate feedback, incentive calculations, and incentive delivery for
39 abstinence. Comparable technology-based treatment delivery platforms have been used to
40 successfully promote smoking abstinence among the general population of U.S. smokers and
41 among other vulnerable populations including rural heavy smokers.²⁰
42
43 The proposed pilot study addresses the following specific aims among Alaska Native women:
44
45 **Aim 1:** Examine the feasibility, efficacy, and cost-effectiveness of a mobile-phone-based
46 incentives intervention for promoting smoking cessation among Alaska Native pregnant women.

1 We will accomplish this aim by randomly assigning 60 pregnant women who smoke to receive
2 best practices for promoting smoking abstinence plus incentives contingent on biochemically
3 verified smoking abstinence or best practices alone. Incentives will be in place from the start of
4 study enrollment through three months postpartum. Primary outcomes will be point prevalence
5 smoking abstinence and continuous abstinence during and following pregnancy. We hypothesize
6 that there will be higher abstinence rates and longer durations of abstinence in the best practices
7 plus incentives versus the best practices control condition.

8
9 **Aim 2:** Evaluate acceptability of the treatment, including barriers to and facilitators of treatment
10 engagement. We will accomplish this aim by assessing treatment enrollment and retention and
11 conducting semi-structured interviews with participants upon treatment completion. During
12 these interviews, participants will be queried about their perceived utility of the incentives for
13 promoting health-related behavior change, and other barriers and facilitators of treatment
14 engagement and success (e.g., social support networks).²¹⁻²² Qualitative research methods will
15 be used to discern general themes.

16
17 Overall, this project has the potential to address disparities in access to efficacious, evidence-
18 based smoking cessation treatments among Alaska Native pregnant women. If the present
19 mobile-phone-based incentives intervention is acceptable and efficacious in this population, this
20 study will provide strong preliminary data for a future R01 proposal to facilitate more
21 widespread dissemination of this innovative treatment model among Alaska Native communities.

22
23 **Objectives:**

24
25 The primary objective is to examine the feasibility, efficacy, and cost-effectiveness of a mobile-
26 phone-based incentives intervention for promoting smoking cessation among Alaska Native
27 pregnant women.

28
29 The secondary objective is to evaluate the acceptability of the treatment, including barriers to
30 and facilitators of treatment engagement.

31
32
33 **METHODS AND PROCEDURES**

34
35 **Study Design:**

36 We are proposing a two condition, parallel groups, randomized controlled pilot study of a
37 mobile-phone-based financial incentives intervention targeting Alaska Native pregnant cigarette
38 smokers. The experimental group will receive financial incentives (i.e., money loaded onto a
39 debit card) contingent on the remote submission of breath carbon monoxide (CO) and saliva
40 cotinine samples indicating smoking abstinence in addition to best practices for promoting
41 smoking cessation. The control group will receive best practices alone. The use of a best
42 practices control group reflects a real-world comparison condition in that all women will receive
43 the treatment that practitioners in the community are instructed to provide (i.e., the 5As plus quit-
44 line referral) thereby enhancing the ecological validity of the study, while also minimizing
45 between-subject variability in the extent of participants' exposure to these practices by
46 implementing these treatment components ourselves (described in greater detail below).

1 Although one common alternative is to use a non-contingent incentives control group which
2 equates both groups in terms of overall earnings, a meta-analysis conducted by UVM researchers
3 showed that non-contingent incentives have no impact on abstinence levels above no-incentive
4 control conditions.⁴⁴

5
6 This subset of 60 Alaska Native women will be randomized separately from the main trial
7 currently underway at UVM. The rationale for a separate arm targeting Alaska Native women,
8 as opposed to including them in the main trial, is that smoking prevalence is substantially higher
9 among this subpopulation (i.e., ~ 36% for AN women [[name] et al. 2018] versus ~ 13% among
10 U.S. pregnant women overall [[name] et al., 2017]), they exhibit unique tobacco use characteristics
11 including use of a homemade smokeless tobacco (Iqmik, Hurt et al., 2009), and very few
12 smoking cessation interventions have been implemented specifically among Alaska Native
13 women ([name] et al., 2010; [name] et al., 2018).

14
15 **Procedures:**

16 **Participants** Study participants will be 60 Alaska Native pregnant women \geq 18 years of age.
17 Participants will be recruited from online media outlets (i.e., Facebook) targeting Alaska Native
18 pregnant women. That is, participants will self-refer after seeing our ads and will complete a
19 screening online or over the telephone with research staff.

20
21 For inclusion in the study, women must meet the following criteria: (a) \geq 18 years of age, (b)
22 report being smokers at the time they learned of the current pregnancy, (c) report smoking in the
23 7 days prior to completing their preliminary eligibility screening, (d) \leq 25 weeks pregnant, (e)
24 speak English, (f) own a smartphone (Android or iOS; 81.8% of pregnant women in wave 1
25 [2013-2014] of the Population Assessment of Tobacco and Health [PATH] reported owning a
26 smartphone). Exclusion criteria include: (a) current or prior mental or medical condition that
27 may interfere with study participation (assessed via self-report during formal intake assessment
28 completed online or by phone using a medical and psychosocial history questionnaire), (b)
29 smoke marijuana more than once each week and not willing to quit (marijuana smoking can
30 inflate breath CO), (c) exposed to unavoidable occupational sources of CO (e.g., car mechanic),
31 (d) report currently receiving opioid maintenance therapy (e.g., methadone, buprenorphine).
32 Women who meet the inclusion criteria and complete the informed consent process will be
33 considered formally enrolled and will be mailed equipment to participate in the study, but will
34 not be randomized until they (1) confirm receipt of their equipment, (2) complete an orientation
35 session on the smartphone app used in the current study (described subsequently), and (3)
36 provide a saliva sample indicating current smoking (i.e., test strip returns a positive for cotinine,
37 a metabolite of nicotine). Upon completing these steps, women will be randomized to either the
38 best practices plus incentives condition or best practices control condition (See Treatment
39 Conditions). The only criteria for withdrawing participants after randomization occurs will be
40 pregnancy termination or fetal demise.

41
42 **General Study Procedures.**

43 **Orientation Session:** After verifying eligibility and completing the informed consent process,
44 participants will be mailed two saliva test kits. Upon receiving the saliva tests, research staff will
45 aid participants in setting up their profile (e.g., create an account, upload profile photo) on the
46 DynamiCare smartphone application (“app”) which is used to submit breath and saliva samples

1 remotely. Participants will be trained in the operation of the app and will have the opportunity to
2 practice submitting saliva samples. The first sample that participants submit upon receiving their
3 saliva test kits will be used to validate smoking status and participants will be withdrawn prior to
4 randomization if they are found to be non-smokers. Women who provide a baseline saliva test
5 validating that they are smokers will be randomized to one of the two treatment conditions, and
6 will be provided with information about that condition and a brief quiz (see attached) as part of
7 their orientation session. The orientation session will be conducted by telephone. Prior to the
8 orientation session, participants will be mailed a CO monitor, additional saliva cotinine test kits,
9 and an instruction manual containing general information about study procedures and where to
10 download the app that they will use during their participation, as well as specific information
11 about how frequently they should submit breath and saliva samples and a schedule of potential
12 earnings. Given that over 80% of pregnant women can be expected to own smartphones, these
13 women will use their existing phone during their participation to increase the ecological validity
14 of using a mobile phone to deliver the intervention. Women who do not own a smartphone but
15 have access to a computer with Internet access may pursue this option instead. We will collect
16 data on the number of participants who use mobile phones vs. computers to participate in the
17 intervention. During the orientation session, participants will also be informed that we will cover
18 the costs of study-related data transfer if they do not have unlimited data plans with their wireless
19 service provider. The purpose of this is to enhance the internal validity of this efficacy study by
20 reducing between subject variability in data coverage. We will also collect data on the number
21 of participants who require assistance paying for data coverage. Other details covered during
22 orientation include instructions specific to the condition to which participants are randomized
23 (e.g., schedule for submitting breath and saliva samples, the schedule of potential earnings, and
24 when the earnings commence). Researchers will read participants an information sheet specific
25 to their treatment assignment (attached), which will be followed by a brief quiz (attached). The
26 purpose of the quiz is simply to verify participant understanding of the condition to which they
27 are randomized. Participants will respond aloud to the quiz questions over the phone and any
28 incorrect answers will be discussed, and they will be invited to ask any additional questions upon
29 completing the quiz. Participants will select a quit date during orientation (either the first
30 Monday following the call or the next Monday), and research staff will contact them by phone
31 on the Friday prior to their quit date. Staff will also inform participants to contact them in the
32 event that their phone is lost, stolen, or broken. In sum, participants who complete the informed
33 consent process will be mailed two saliva test kits to verify their smoking status prior to being
34 assigned to one of the two treatment conditions. Two tests will be sent in case participants' first
35 sample is invalid (e.g., insufficient saliva to produce a reading) and they need to complete a
36 second test to verify smoking status. Participants who are verified to be smokers will then
37 complete the treatment assignment phone call, after which study staff will provide them with the
38 equipment that they will need for the remainder of the study (e.g., breath CO monitor and
39 additional saliva test kits).

40
41 **Mobile-Phone Based Financial Incentives:** The intervention will be delivered on participants'
42 smartphones via an app installed on their phone either before or during the orientation session.
43 The process of submitting a video entails the following steps: (1) Participant opens the app,
44 which requires them to type in a password. Their username and password (stored as a secure,
45 “irreversible” one-way hash) will be stored in a configuration file accessible only to the
46 application; (2) The app will verify the password and participants will be taken to the “home”

1 screen which will show their cumulative earnings to date and a “post video” button; (3) The app
2 will attempt to contact the server over the Internet (via a 3G/4G mobile network) to determine
3 the correct time and status of the participant; (4) The participant will click on the post video
4 button, thereby leading them to a simple interface for recording videos that contains a start/stop
5 recording toggle button, a play button to review the recorded video, and a post button to send the
6 video to the server; (5) After posting the video, the server will display a voucher based on the
7 voucher schedule cached from the prior video upload. The app will then create a text file
8 containing a timestamp and video file. These files will be archived, compressed, and encrypted
9 to prevent tampering and/or eavesdropping while in transit. The app will maintain a file lock on
